- 1) To determine the correlation between glucose readings using the ANICGM an AccuChek Inform II blood glucose meter in patients with type 2 diabetes at baseline and after ingestion of a glucose load throughout a complete glucose excursion

-Rationale: a continuous glucose monitor needs to capture rapid postprandial glucose increases and returns to baseline levels

- 2) To ascertain if the ANICGM calibration is maintained up to 14 days

-Rationale: the ANICGM is being developed for use for multiple days

Note: The results from the ANICGM meter will not be used to guide any aspect of the patient's treatment course.

Description of the technology

The ANICGM uses a weak electromagnetic field generated by its wrist band sensor to look into the body to produce a spectrum that provides a measurement of blood glucose present in the wrist area of the body. The core sensing technology used is dielectric spectroscopy, and has been shown capable of measuring blood glucose, non-invasively, in a laboratory environment (1-3). The system uses proprietary and patented dielectric materials and signal processing to enhance performance in both selectivity and sensitivity for blood glucose measurement.

Much like how a MRI uses a strong magnetic field and its interaction with the body to create a picture of what is inside, the ANICGM uses a safe weak low frequency radiofrequency field to take a picture of a person's chemical spectrum, some of it specific only to blood glucose.

The device sends and receives back signals from the wrist area that are used to generate a dielectric spectrum once every 6 seconds. This spectral data is stored on the device, and then downloaded wirelessly or through USB port to an Alertgy laptop. The POC BG using the Accuchek Inform II will be used to provide calibration values for the ANICGM every 5 minutes in mg/dL, during the calibration process. The POC BG levels will be entered into the Alertgy laptop and a proprietary calibration program will be used to analyze the spectral data collected and will generate a calibration algorithm. The Alertgy support team will provide the ANICGM data to compare to the POC BG data they collected concurrently during the tests.

Description of the device

The present band is about 5 inches long made out of inert plastic material. It is applied to the wrist area and adjusted to a snug fit. All of the materials that make contact with the body are inert. A photo is included below.

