The timing of the fingerstick blood glucose checks outlined below are approximate, as there might be occasions where the fingerstick might not be performed at the exact minute specified (for example, patient needing to go to restroom, issues with the Accuchek Inform II glucose meter, etc). Every effort will be made to do the fingerstick at the specified time.

Subject fasts overnight, then proceeds to Cleveland Clinic Main Campus Adult Endocrinology clinic at F20.

Vital signs will be taken.

Women with childbearing potential will have a urine pregnancy test before each study.

Patients will be asked to bring diabetes medications (and related devices) if requiring injections to F20.

If a subject is on basal insulin, the subject will take the basal insulin as close to the usual time as possible.

A baseline fingerstick blood glucose (BG) will be taken using the clinic's Accuchek Inform II glucose meter (time -60 min); this is needed to determine eligibility.

If BG 70-150 mg/dL subject will hold their morning medications or delay taking their diabetes medication until after the procedure (except for basal insulin as above) upon instructions of the investigator.

If BG 151-250 mg/dL, subject will take their diabetes medication at the usual time to prevent symptomatic hyperglycemia.

The ANICGM will be placed on the wrist. Measurements from the ANICGM start immediately. There will be a period of 20 minutes to allow the ANICGM to stabilize to body temperature.

Fingerstick BG will be repeated at time -30 min, -15 min, and 0 min for baseline validation.

At time 0 min, subjects ingest 75 g oral glucose drink (GlucoCrush)

For Visit 1:

Since the ANICGM is using new technology that depends on calculating the slope of the fingerstick glucose change to individualize the calibrations, it is crucial to have frequent fingersticks during Visit 1 for the first hour after the glucose challenge (GlucoCrush).

After the GlucoCrush, fingerstick BG will be done every 5 minutes for 2 hours.

Other continuous glucose devices have done monitoring as frequently as this (see attachment, figure 7, from Choi H, Naylor J, Luzio S, Beutler J, Birchall J, Martin C, Porch A. Design and *In Vitro* Interference Test of Microwave Noninvasive Blood Glucose Monitoring Sensor. IEEE Trans Microw Theory Tech. 2015 Oct 1;63(10 Pt 1):3016-3025)

For Visit 2 and Visit 3:

Fingerstick BG will be taken every 15 minutes for 2 hours after ingestion of GlucoCrush

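### Visit 1 fingersticks that calibrate the device also count as validation pairs, and no rule keeps them out of the pooled error rates or limits of agreement

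*Combined protocol and SAP*

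**What the plan says.** **Calibration.** Under Description of the technology, the Accuchek fingersticks "will be used to provide calibration values for the ANICGM every 5 minutes in mg/dL, during the calibration process". The values are entered into the device company's laptop, where "a proprietary calibration program will be used to analyze the spectral data collected and will generate a calibration algorithm". The section then states: "The Alertgy support team will provide the ANICGM data to compare to the POC BG data they collected concurrently during the tests".

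**Where calibration happens.** The Visit 1 instructions say the device "depends on calculating the slope of the fingerstick glucose change to individualize the calibrations" and that "it is crucial to have frequent fingersticks during Visit 1 for the first hour after the glucose challenge". Visit 1 then has post-load fingersticks at 5-minute intervals for 2 hours. For the other two visits, "Fingerstick BG will be taken every 15 minutes for 2 hours after ingestion of GlucoCrush".

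**Other readings.** At every visit, "Fingerstick BG will be repeated at time -30 min, -15 min, and 0 min for baseline validation".

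**Analysis.** The Sample Size section plans up to 24 pairs per subject at Visit 1 and 8 at each follow-up visit, in 10 to 15 subjects. If no Clarke grid errors occur, it states upper bounds of 0.5% overall, on 600 measures, and 5% within subject. The Statistical analysis section plans Clarke error rates with 95% limits for all data, for each subject and for each day within subject, and Bland-Altman limits adjusted for repeated measures. It does not mention calibration pairs.

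**Aim.** The second specific aim is: "To ascertain if the ANICGM calibration is maintained up to 14 days".

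**The concern.** A pair whose fingerstick value was used to fit the algorithm does not test that algorithm. Agreement at such a pair is at least partly goodness of fit. It validates neither the readings (the general aim) nor the durability of the calibration (the second specific aim). Pooling fitted pairs with later ones is expected to make the device look better than it would on readings it has not been tuned to.

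The plan does not say which Visit 1 fingersticks enter the calibration, nor that the algorithm is frozen afterwards. The device company runs the proprietary program and supplies the device readings, so the study team cannot recover this from the data unless it is specified and documented. The section on the relationship between the two organisations also makes exercise of a convertible note depend on whether the work shows that the technology functions. A pooled figure that mixes fit and validation is a poor basis for that decision.

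**Working it through.** **Inputs.** From Sample Size: 24 post-load pairs per subject at Visit 1, 8 at Visit 2, 8 at Visit 3; 10 to 15 subjects; the rule of three, where the upper 95% bound with zero errors in n independent pairs is about 3/n.

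**Reproducing the plan's figure.** Pairs per subject = 24 + 8 + 8 = 40. With 15 subjects, n = 15 × 40 = 600 and 3/600 = 0.50%. The exact value, 1 − 0.05^(1/600), is 0.498%. The 0.5% is therefore reproduced, but only with every Visit 1 post-load pair included. Visit 1 supplies 15 × 24 = 360 of the 600 (60%).

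**Which pairs are fitted.** The documents do not say, so two scenarios follow, both assuming no recalibration at Visits 2 and 3. They are scenarios, not limits.

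- First hour of Visit 1 fitted: 60/5 = 12 pairs, a share of 12/40 = 30%. Pairs left per subject: 28.
- All Visit 1 post-load pairs fitted: 24/40 = 60%. Pairs left per subject: 16.

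**Zero-error bounds, post-load pairs only.**

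| Pairs used | Per subject | 15 subjects | 10 subjects |
|---|---|---|---|
| All | 40 | 3/600 = 0.50% | 3/400 = 0.75% |
| First hour of Visit 1 removed | 28 | 3/420 = 0.71% | 3/280 = 1.07% |
| Visits 2 and 3 only | 16 | 3/240 = 1.25% | 3/160 = 1.88% |

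At equal numbers of subjects the bound grows by 40/28 = 1.43 or 40/16 = 2.5.

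**If the three baseline pairs per visit also count and none is fitted.** Pairs per subject become 40 + 9 = 49, 28 + 9 = 37 and 16 + 6 = 22.

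- 15 subjects: 3/735 = 0.41%, 3/555 = 0.54%, 3/330 = 0.91%.
- 10 subjects: 3/490 = 0.61%, 3/370 = 0.81%, 3/220 = 1.36%.

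**Within-subject figure.** On all 40 pairs the rule gives 3/40 = 7.5%, not the stated 5%, which would need 3/0.05 = 60 pairs. On Visits 2 and 3 it gives 3/16 = 18.75%. For a single follow-up day in one subject it gives 3/8 = 37.5%.

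**Effect on an observed pooled error rate.** Let f be the fitted share and r the error rate in unfitted pairs. If fitted pairs carried no errors (an assumption), the pooled rate is (1 − f) × r: 0.70 r for f = 30% and 0.40 r for f = 60%. If fitted and unfitted rates are equal, there is no effect. The documents do not show where in that range the truth lies, and they give no basis for a similar figure for the Bland-Altman limits.

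All these bounds treat pairs as independent, as the plan does. Repeated pairs within a subject are correlated, so they are best cases.

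**The case against.** **The 600 is a planning count, not an analysis set.** True. But the analysis text defines no narrower set, and its pooled results carry no restriction. Read as written, Visit 1 is in.

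**The rates by day within subject already separate the visits.** They do, and a point estimate for Visits 2 and 3 could be built by summing cells. But each cell has 8 post-load pairs, no estimate pooled across subjects is stated for those days, and the overall and by-subject rates stay mixed. It is unclear whether the same breakdown applies to the limits of agreement.

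**No distortion has been demonstrated.** This stands as a limit on size: the effect on the error rate could be nil. It does not rescue the rule, because the plan gives no way to find out.

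**Restricting to Visits 2 and 3 may discard valid pairs.** If only the first hour is fitted, 12 second-hour pairs per subject (180 with 15 subjects) are unfitted. Those pairs come from the same session as the calibration and say nothing about durability; they can be reported under their own label. Visits 2 and 3 repeat the baseline readings, glucose load and 2-hour sampling, so they also serve the first aim.

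**A single calibration can be inferred.** The second aim and the Visit 1 text point that way, and the preliminary data are labelled as using one calibration. That label describes earlier laboratory work. No text states a lock for this study.

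**By-subject precision gets worse.** This stands, and the within-subject bound has to be restated too.

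**Conclusion.** The concern holds. The plan ties the 5-minute Visit 1 fingersticks to calibration, reaches its 600 only by counting all of them, and never excludes fitted pairs from the pooled Clarke rates or the limits of agreement. Followed as written, its headline results mix fit with validation. This must be fixed before analysis.

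What is certain is the overlap and the missing exclusion. The fitted share (30% or 60% in the two scenarios) depends on which fingersticks are used and on there being no later recalibration. The 0.5% is a conditional planning figure and not a success criterion, but it is the only precision stated for the pooled error rate. On the pairs that answer the second aim it becomes 1.25% with 15 subjects or 1.88% with 10, before any allowance for within-subject correlation.

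**What to change.** 1. State which Visit 1 fingersticks enter the calibration.
2. State that the algorithm is fixed after Visit 1 and that no Visit 2 or 3 fingerstick is entered into it.
3. Base the main Clarke error rates and Bland-Altman limits, pooled across subjects and by subject, on Visit 2 and 3 pairs.
4. Report Visit 1 separately, with fitted pairs labelled as calibration fit and any others as same session, not fitted.
5. Restate the overall bound on the pairs used: 240 post-load pairs with 15 subjects or 160 with 10. Say whether the baseline pairs count (330 or 220 if they do).
6. Restate the within-subject figure in the same sentence.
7. Note that the bounds assume independent pairs and are a best case.

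**Cost.** The analysis set and the Sample Size and Statistical analysis wording change; no new visits, fingersticks or subjects are needed. The device company must follow and document the lock. The stated precision becomes less favourable, most visibly within subject.

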(This is the current model. An improved version may be available at the time of the study).

Cleveland Clinic staff will be trained by a written instruction manual in the application and use of the device by Alertgy staff on site. As the device is automated and noninvasive, it is anticipated that the training period will take no longer than two hours maximum.

Preliminary data

[figure not shown]
Data from Alertgy in the graph below shows testing of 8 subjects in their lab showing correlation between the ANICGM (y-axis) and the Abbott Freestyle Neo glucometer (x-axis).

Of the 8 subjects, 3 had type 2 diabetes (2 of whom are on insulin), 2 had prediabetes, and 3 did not have prediabetes or diabetes.

Pearson's correlation was used, $R^2= 0.993$.

Clarke Error Grids

- 8 Subjects
- Single Calibration Method

Inclusion Criteria

Type 2 diabetes on diet or on pharmacologic treatment for diabetes

Hemoglobin A1c (HbA1c) 7.5-10.0%

- below 7.5%, there may not be a demonstrable blood glucose spike
- above 10.0%, subjects are more likely to be symptomatic from hyperglycemia and require treatment during the study

Age 18-75 years old

Exclusion Criteria

Patients taking prandial insulin

Fasting blood glucose by fingerstick <70 mg/dL or >250 mg/dL. Hypoglycemia <70 mg/dL will be treated according to clinic protocol.

Pregnancy

ESRD

Decompensated or acute heart failure

Medications that might cause false readings with glucose meters: acetaminophen, ascorbic acid, dopamine, maltodextrin, mannitol

Conditions that limit the ANICGM such as lesions on the forearms

Other conditions that the investigators deem will affect the conduct of the study

Protocol

There are 3 study visits: Visit 1, Visit 2 (3-14 days after Visit 1) and Visit 3 (5-14 days after Visit 1)

Alertgy personnel will undergo the onboarding process utilized by CCF Innovations called Silkroad/Red Carpet. Personnel undergoing this process complete 8 Comet modules (code of conduct, corporate complaints, HIPPA overview and HIPPA & IS Security Awareness, Emergency Management, Environment of Care, Patient Safety and Energy Savings).

Study Calendar

	Visit 1	Visit 2	Visit 3
	Day 1	3-14 days	5-14 days
Informed Consent	X		
Inclusion/Exclusion	X		
Medical History	X		
Urine Pregnancy Test *	X	X	X
Vitals	X	X	X
Comorbidities	X		
Adverse Events Assessment	X	X	X
Medication Review	X	X	X
Ingest GlucoCrush	X	X	X
Glucose Collection (Fingersticks)	X	X	X

*Women with childbearing potential

For all study visits

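### Nothing masks the manufacturer to the Visit 2 and Visit 3 fingersticks before it supplies the device values that must answer Aim 2

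*Combined protocol and SAP*

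**What the plan says.** Aim 2 (Specific aim) is "To ascertain if the ANICGM calibration is maintained up to 14 days". Visit 2 falls 3 to 14 days, and Visit 3 falls 5 to 14 days, after Visit 1 (Protocol).

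The data flow is in the Description of the technology. For the spectra: "This spectral data is stored on the device, and then downloaded wirelessly or through USB port to an Alertgy laptop". The fingerstick meter is to "provide calibration values for the ANICGM every 5 minutes in mg/dL, during the calibration process". Then: "The POC BG levels will be entered into the Alertgy laptop and a proprietary calibration program will be used to analyze the spectral data collected". That program generates the calibration algorithm. The section ends: "The Alertgy support team will provide the ANICGM data to compare to the POC BG data they collected concurrently during the tests".

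Fingersticks are every 5 minutes for 2 hours after the load at Visit 1, and every 15 minutes for 2 hours at Visits 2 and 3. The dense Visit 1 schedule is justified by the need to individualize the calibration. At all visits, "Fingerstick BG will be repeated at time -30 min, -15 min, and 0 min for baseline validation". The preliminary data carry the label "Single Calibration Method".

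The Statistical analysis section plans Bland-Altman plots with limits of agreement, and Clarke error rates with 95% confidence limits overall, by subject and by day within subject. It does not say who holds which data when the device values are produced.

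**The concern.** In a validation study, the test readings should be fixed before the people who produce them can see the reference readings. Here the device values are not described as read from the band at the visit. They come from stored spectra, processed on the manufacturer's laptop and supplied by the manufacturer's team.

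Aim 2 depends on Visits 2 and 3, because Visit 1 fingersticks feed the calibration and cannot show whether it lasts. If spectra from the later visits were chosen or reprocessed with the fingersticks in view, drift could be hidden. The Clarke error rates and limits of agreement for those days would then not be a clean test of the carried-forward calibration.

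**Working it through.** **1. Is one Visit 1 calibration implied?** Four places point that way:

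- Aim 2 asks whether calibration is maintained, which presupposes one that is not remade.
- Calibration values come every 5 minutes, and only Visit 1 has that schedule.
- The Visit 1 section ties individual calibration to the Visit 1 fingersticks.
- The baseline checks at every visit are described as validation, not calibration.

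The preliminary-data label agrees, but it describes earlier laboratory work and is weak evidence for this study. Together these make a single calibration the natural reading. No sentence states that it is applied unchanged at Visits 2 and 3.

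**2. Is the manufacturer masked to the Visit 2 and 3 reference?** The sentence on laptop entry follows the one on 5-minute calibration values, so it may cover Visit 1 only; it names no visit. In the closing sentence, the word for who collected the fingersticks has two readings:

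| Reading | Consequence |
|---|---|
| The manufacturer's team | It holds the reference when it supplies the device values |
| The clinic | The clinic holds the reference, but nothing says when it may be shared |

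Neither reading supplies a safeguard.

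**3. Is there room for choice without refitting?** The device produces a spectrum every 6 seconds. Between two Visit 2 or 3 fingersticks, 15 minutes apart, that is 900 / 6 = 150 spectra. The documents do not say which of them form the paired value, or how unusable ones are handled. The proprietary program may fix this; the documents do not say.

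**4. How much data is affected?** The inputs are the visit schedules and the Sample Size section (10 to 15 subjects; 24, 8 and 8 pairs per subject).

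- The plan's own count: 120 / 5 = 24 and 120 / 15 = 8; 15 × (24 + 8 + 8) = 600. The rule of three gives 3 / 600 = 0.5%. Both reproduce, at the top of the enrolment range.
- Visits 2 and 3 per subject: 8 + 8 = 16.
- At 15 subjects: 15 × 16 = 240 of 600 (40%).
- At 10 subjects: 10 × 16 = 160 of 10 × 40 = 400 (40%).

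The plan's count leaves out the three baseline checks per visit. Adding them gives 2 × (8 + 3) = 22 per subject over Visits 2 and 3. That is 15 × 22 = 330 of 15 × (27 + 11 + 11) = 735, or 220 of 490 with 10 subjects (45% in both cases).

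These figures are the amount of data exposed, not the size of a bias. Nor are the remaining pairs sound evidence for Aim 2, since they come from the calibration visit.

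**The case against.** The strongest reply is that the plan already settles the matter in substance. A calibration regenerated at Visit 2 or 3 would not be a maintained one, so refitting would contradict Aim 2. The laptop-entry sentence, read in context, concerns calibration values, and no section says that Visit 2 and 3 fingersticks are entered there. The eligibility check uses the clinic's own meter and clinic staff are trained to use the band, so a reading in which the clinic holds the reference is at least as natural. The study is also small, has no formal power calculation, and is called proof of concept.

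Most of this stands. It disposes of the tempting stronger reading, that the plan permits or intends recalibration at the follow-up visits. It also lowers the likelihood of harm. It does not supply the missing control: a clinic-held reference protects the comparison only if it is withheld until the device values are in, and a fixed calibration does not by itself fix which spectra are used.

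A second fair point is that a release log alone would miss a practical route. Manufacturer personnel are listed as required to set up the device, train staff on site and are onboarded to the clinic. The documents do not say whether they attend the visits; if they do, they could see results as they are taken. The remedy has to cover this.

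**Conclusion.** The point holds as a gap in safeguards. A carried-forward Visit 1 calibration is strongly implied, but nothing masks the manufacturer to the Visit 2 and 3 fingersticks before it supplies its values for those visits. What is left open is selection or reprocessing of spectra with sight of the reference. It touches all the data that can answer Aim 2: 16 post-load pairs per subject, 240 of 600 at 15 subjects or 160 of 400 at 10. The direction would favour the device, on the assumption that choices made with sight of the reference move towards agreement. The size cannot be computed from the documents.

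A reader might also infer bad faith, because the section on the relationship between the parties makes the clinic's exercise of a $23,000 convertible note depend on whether the technology is validated. The documents do not support that inference. The arrangement only makes a written safeguard more useful.

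The change should be made: it is cheap and it protects the evidence for one of the two aims. Confidence is medium, because the clinic may in practice already hold the reference data.

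**What to change.** State in the protocol:

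1. Only Visit 1 fingersticks are entered on the manufacturer's laptop. Each subject's Visit 1 calibration and software version are applied unchanged at Visits 2 and 3. A dated version identifier per subject (10 to 15 records) is enough; a file checksum is optional, since it adds little once the reference is withheld. The proprietary file need not be released. The record must predate release of that subject's Visit 2 and 3 fingersticks; it need not delay Visit 2, because the spectra are stored.
2. Clinic staff record the Visit 2 and 3 fingersticks and keep full access to them. They do not show or release them to manufacturer personnel, including any on site, until the manufacturer has delivered complete, time-stamped device values for those visits, with rejected or missing spectra marked.
3. The last sentence on data flow in the Description of the technology is reworded to say who collected the fingerstick data.

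The cost is protocol wording, a dated release log, and some care on visit days if manufacturer personnel are present. No visits or fingersticks are added. The real downside is that the manufacturer cannot troubleshoot against Visit 2 and 3 reference data during the study.

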Other continuous glucose devices have done monitoring as frequently as this (see attachment, figure 8, from Choi H, Naylor J, Luzio S, Beutler J, Birchall J, Martin C, Porch A. Design and *In Vitro* Interference Test of Microwave Noninvasive Blood Glucose Monitoring Sensor. IEEE Trans Microw Theory Tech. 2015 Oct 1;63(10 Pt 1):3016-3025)

For all study visits

Wrist device is removed after each study visit. In-between patients, either same or different day, the device will be cleaned by using Super Sani Cloth wipes, which are the disinfectants we have in the endocrine clinic (active ingredients: dimethyl ethylbenzyl ammonium chloride, isopropyl alcohol)

[figure not shown]

Fig. 7. OGTT I. The sensor response (here the change in bandwidth) is compared with blood glucose levels measured using a “blood-strip” glucometer (Bayer CONTOUR).

[figure not shown]

Fig. 8. OGTT II. Sensor data (change in bandwidth) are measured over a continuous 12-h period involving three food ingestions, and are compared with data from a continuous glucose meter (Medtronic Guardian CGM) and blood-strip glucometer (Bayer CONTOUR), after [27].

Sample Size

It is expected that 10-15 subjects will be enrolled, and that there will be up to 24 paired measures on Visit 1 (every 5 minutes for 2 hours), and 8 paired measures (every 15 minutes for 2 hours) each of the follow-up days. If no errors on the Clarke error grid are observed (as in the preliminary data), the error rate based on the “rule of three”, will be constrained to be no more than 0.5% overall (based on 600 total measures), and no greater than 5% within subject (Jovanovic and

Levy, 1997). Confidence limits for the agreement will depend on the within and between subject variability measures, so formal power calculations on this measure of agreement is not possible.

Statistical analysis

Agreement between glucose measures between systems will be evaluated graphically using Bland-Altman plots, and Clarke error grids. Error rates from the Clarke error grid will be calculated, and 95% confidence limits will be calculated overall, by subject and by day within subject. Similarly, limits of agreement from the Bland-Altman plots will be adjusted to account for repeated measures, as described by Bland and Altman (2007). Analysis will be performed using SAS software (version 9.4; Cary, NC).

Possible adverse effects

The materials for the wrist band are inert and the potential for allergy is low.

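### Aim 2 asks whether calibration holds up to 14 days, but both follow-up visits may be over by day 5 and no planned analysis pools agreement across subjects by visit or elapsed days

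*Combined protocol and SAP*

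**What the plan says.** The second item under Specific aim is "To ascertain if the ANICGM calibration is maintained up to 14 days".

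The Protocol section sets the schedule: "There are 3 study visits: Visit 1, Visit 2 (3-14 days after Visit 1) and Visit 3 (5-14 days after Visit 1"). The Study Calendar repeats these windows. Nothing in the document requires a visit near day 14, sets a gap between Visits 2 and 3, or spreads subjects over the window.

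Under Sample Size, "It is expected that 10-15 subjects will be enrolled", with "up to 24 paired measures on Visit 1 (every 5 minutes for 2 hours), and 8 paired measures" on each follow-up day.

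Under Statistical analysis, Clarke grid errors are to be counted and "95% confidence limits will be calculated overall, by subject and by day within subject". Bland-Altman limits of agreement will be adjusted for repeated measures. The linking word (similarly) may mean that the same three levels apply to those limits, but the text is ambiguous.

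The role of Visit 1 has to be inferred. Description of the technology says the fingerstick meter will "provide calibration values for the ANICGM every 5 minutes in mg/dL, during the calibration process". Only Visit 1 has fingersticks every 5 minutes, and the Visit 1 instructions explain that, "to individualize the calibrations, it is crucial to have frequent fingersticks during Visit 1". This points to Visit 1 as the calibration visit, though the document does not say so outright.

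**The concern.** If calibration is set at Visit 1, only Visits 2 and 3 can show whether it lasts, and the later part of the 14 days is the hardest test. The schedule allows late observations but does not secure them. The two follow-up windows share days 5 to 14, so visit number is also a poor guide to elapsed time.

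The analysis has a matching gap. The overall and by-subject rates mix follow-up data with a larger amount of Visit 1 data, so good agreement at Visit 1 can dilute later drift. The by-day split keeps the days apart, but only inside one subject and on few pairs. The trial could follow its plan exactly and still be unable to say whether calibration held beyond the first days. Pooling by visit or day could be added later, but it would then be chosen after the data were seen. The section on the relationship between the company and the clinic ties a financial decision to whether the work validates the device, which is a further reason to fix the summary beforehand.

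**Working it through.** **Inputs.** From Sample Size: 10-15 subjects, 24 pairs at Visit 1 and 8 at each follow-up visit. From Protocol and Study Calendar: Visit 2 at 3-14 days and Visit 3 at 5-14 days. From Statistical analysis: 95% limits overall, by subject, and by day within subject. The scheduling distributions and within-subject correlations below are assumptions; the document gives neither.

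**1. The plan's own figure.** Pairs per subject: 24 + 8 + 8 = 40. With 15 subjects, 15 × 40 = 600. The rule of three gives 3/600 = 0.5%, as stated (exact: 1 − 0.05^(1/600) = 0.498%). The overall figure reproduces.

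**2. Share from Visit 1.** 24/40 = 60%, or 15 × 24 = 360 of 600 pairs.

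**3. What the windows guarantee.** Visit 2 on day 3, 4 or 5 with Visit 3 on day 5 is compliant, so guaranteed pairs after day 5 number zero. Of the 12 × 10 = 120 combinations of days that the windows permit, 10 + 12 − 1 = 21 include day 14.

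**4. What scheduling might deliver.**
- Visit 3 uniform over days 5-14 (assumption): the chance of days 12-14 is 3/10 = 30%, or 4.5 of 15 subjects. The chance that nobody is seen then is 0.7^15 = 0.5% with 15 subjects and 0.7^10 = 2.8% with 10.
- All day combinations with Visit 2 before Visit 3 equally likely (assumption): there are 2 + 3 + … + 11 = 65. Those with Visit 3 on days 12-14 number 9 + 10 + 11 = 30, and 30/65 = 46%, or 6.9 of 15 subjects.

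**5. Precision of the planned by-day cell.** With zero errors in 8 independent pairs:
- one-sided 95% upper bound: 1 − 0.05^(1/8) = 31.2%;
- two-sided: 1 − 0.025^(1/8) = 36.9%;
- chance of seeing no error when the true rate is 10%: 0.9^8 = 43%.

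**6. Precision if follow-up is pooled by visit, with Visit 3 held late.** With zero errors before clustering:
- 15 subjects: 15 × 8 = 120 pairs; 1 − 0.05^(1/120) = 2.5% one-sided, 1 − 0.025^(1/120) = 3.0% two-sided;
- 10 subjects: 10 × 8 = 80 pairs; 1 − 0.05^(1/80) = 3.7% one-sided.

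For clustering, divide the pairs by the design effect 1 + 7r and apply the one-sided formula to the result:

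| Assumed r | Design effect | 15 subjects: effective pairs, bound | 10 subjects: effective pairs, bound |
|---|---|---|---|
| 0.1 | 1.7 | 70.6, 4.2% | 47.1, 6.2% |
| 0.3 | 3.1 | 38.7, 7.4% | 25.8, 11.0% |
| 0.5 | 4.5 | 26.7, 10.6% | 17.8, 15.5% |

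**The case against.** The strongest reply is that a trial with no late data is improbable. Under the scheduling assumptions above, the chance that no subject is seen at 12-14 days is at most 2.8%. The aim says up to 14 days, not at day 14, and a spread of follow-up days could support an analysis by elapsed time without moving any window. This stands in part: late data are likely, and a 12-14 day window is one design among several. But the amount of late data, and so its precision, remains uncontrolled, and no analysis by elapsed time is planned.

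A second reply is that a time-resolved analysis already exists in the by-day split, and that Bland-Altman differences, being continuous, may show drift that error counts miss. The split does separate later days from Visit 1 and could reveal gross drift in a subject. Even if it extends to the limits of agreement, it gives no summary across subjects.

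A third is that 8 pairs understates a follow-up day, because fingersticks are also taken at −30, −15 and 0 minutes with the device on. If those count as pairs (an assumption, since Sample Size counts 8), there are 11. The zero-error bound is then 1 − 0.05^(1/11) = 23.8% one-sided, a 10% error rate is missed 0.9^11 = 31% of the time, and the Visit 1 share is 27/49 = 55%. These figures are somewhat better, but the conclusion is the same.

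Finally, nothing says the overall rate is meant to answer Aim 2. That is fair, but then no across-subject figure answers it.

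**Conclusion.** The concern holds. The windows guarantee no observation later than 5 days after Visit 1, and no stated analysis summarises agreement across subjects by follow-up visit or elapsed days. Both facts come directly from the text and need no assumption. The one time-related split has an upper bound of about 31% one-sided when no error is seen, so it cannot support a claim that calibration was maintained. Pooling one late visit across subjects would bring that to roughly 4% to 11% with 15 subjects, or 6% to 16% with 10, for assumed correlations of 0.1 to 0.5. The pooled bound describes the average error rate across subjects, not each subject's own.

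The expected share of subjects seen late (30% to 46%) rests on assumed scheduling. The point about the 60% share rests on reading Visit 1 as the calibration visit. This is a change that should be made: one of the two specific aims may go unanswered late in the period even if the protocol is followed exactly.

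**What to change.** 1. Separate the follow-up windows so that Visit 3 falls near the end of the claimed period, for example 12-14 days after Visit 1, with Visit 2 earlier.
2. In Statistical analysis, add bias, limits of agreement and Clarke error rate for Visit 2 and for Visit 3 separately, pooled across subjects, with confidence limits that allow for clustering by subject. State beforehand what result would count as calibration maintained.
3. Optionally, relate the device-minus-fingerstick difference to actual days since Visit 1. This becomes the more useful summary if the windows stay as they are, because visit number then says little about elapsed time.
4. If the windows are kept, limit the Aim 2 conclusion to the days actually observed.

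The cost is a minor protocol amendment and a few sentences of analysis text, with no added visits or fingersticks. The drawbacks are less scheduling flexibility, possibly a few out-of-window visits, and fewer mid-period readings. Item 4 alone needs no change to the visits.
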